Summary Table of Study Protocol

Title	A Multi-country Prospective Observational Study to Describe Calcimimetic Use in Haemodialysis Patients
Protocol version identifier	Protocol Amendment 3, Version 4.0
Date of last version of the protocol	11 June 2019
EU Post Authorization Study (PAS) Register No	EUPAS18923
Active Substance	Etelcalcetide Cinacalcet
Medicinal Product	Parsabiv® Mimpara®
Product Reference	EMA/H/C/003995 EMA/H/C/000570
Procedure Number	N/A
PASS	No

Research Question and Objectives
	
How are calcimimetics used in routine practice in haemodialysis (HD) patients? Primary objective
 
 - To describe the proportion of patients discontinuing calcimimetic treatment at 3-monthly intervals up to 18 months following treatment initiation 
Secondary objectives
 
 - To describe characteristics of haemodialysis (HD) patients at time of calcimimetic initiation (demographics, clinical history, dialysis treatment and laboratory parameters) - To describe clinical management of HD patients over time (calcimimetic use, secondary hyperparathyroidism (sHPT) medication use, and dialysis treatment) - To describe levels of parathyroid hormone (PTH), corrected calcium (cCa), phosphate (P) and other relevant laboratory parameters in HD patients over time - To describe the proportion of HD patients achieving KDIGO (Kidney Disease Improving Global Outcomes) target for PTH over time - To describe hypocalcemia incidence, risk factors and therapeutic responses - To describe the frequency of events of interest (nausea, vomiting, hospitalisations, parathyroidectomy, kidney transplant after calcimimetic initiation, fractures, and cardiovascular events)

Country(-ies) of Study
	
European countries, Israel, and Russia

Author
	
Amgen: PPD [REDACTED] [REDACTED] External: PPD [REDACTED]

Marketing Authorization Holder

Marketing authorization holder(s)
	
Amgen Europe B.V. [name]

MAH Contact
	
PPD [REDACTED] Amgen GmbH [name] PPD [REDACTED]

Confidentiality Notice

This document contains confidential information of Amgen Inc.

This document must not be disclosed to anyone other than the site study staff and members of the Institutional Review Board/Independent Ethics Committee/Institutional Scientific Review Board or equivalent, as applicable.

The information in this document cannot be used for any purpose other than the evaluation or conduct of the research without the prior written consent of Amgen Inc.

If you have questions regarding how this document may be used or shared, call the Amgen Medical Information number: Amgen's general number in the US ([name]).

Investigator's Agreement

I have read the attached protocol entitled "A Multi-country Prospective Observational Study to Describe Calcimimetic Use in Haemodialysis Patients", dated **6 March 2020**, and agree to abide by all provisions set forth therein.

I agree to ensure that the confidential information contained in this document will not be used for any purpose other than the evaluation or conduct of the clinical investigation without the prior written consent of Amgen Inc.

[figure not shown]
Signature

Name of Investigator

Date (DD Month YYYY)

Study Design Schema

SITE LEVEL

^a Only patients initiating calcimimetic between date of site-specific etelcalcetide access (Month X) to **30 November 2019 or date of site evaluation (Month Y), whichever occurs last**, are eligible for study enrolment.

^b Eligible patients are:

[figure not shown]
- Calcimimetic naïve cinacalcet patients; or
- Etelcalcetide patients who initiate treatment and may or may not have a history of prior cinacalcet use

*Site-specific etelcalcetide access is defined as date of site availability of etelcalcetide (e.g. known date of first drug order or date of first drug administration).

**An interval of at least 6 months must elapse between etelcalcetide becoming accessible at the site to be eligible for evaluation for study participation.

***The end of study date at the site will be 18 months after the last subject initiated Calcimimetic^b at the site (Month Z).

PATIENT LEVEL

^a 6 months of data (e.g. laboratory parameters) prior to date of calcimimetic initiation (Month 0) and 18 months of data following calcimimetic initiation will be collected. A total of 24 months of data will be collected for each patient.

^b Individual patients may be enrolled at any time after date of site-activation (Month A; site activation occurs after site evaluation)

*Chart abstraction will be carried out part retrospectively (i.e. data prior enrolment) and part prospectively (i.e. data after enrolment).

IEC	Independent Ethics Committee
ICF	Informed Consent Form

i.v.	Intravenous
KDIGO	Kidney Disease Improving Global Outcomes
KM	Kaplan-Meier
LDL	Low density lipoprotein
NTx	N-telopeptide
P	Phosphorous
PTH	Parathyroid hormone
RCT	Randomised controlled trial
RRT	Renal replacement therapy
SAP	Statistical Anlaysis Plan
SHPT	Seconday hyperparathyrodism
TIW	Three times a week
UK	United Kingdom
ULN	Upper limit of normal
US	United States
WBC	White blood cell

3. Responsible Parties

Role	Contact Details
Sponsor	Amgen Inc [name]
Principal Investigator	PPD Division of Nephrology and Immunology Uniklinik, Rheinisch-Westfälische Technische Hochschule Aachen [name]

4. Abstract

- **Study Title:** A Multi-country Prospective Observational Study to Describe Calcimimetic Use in Haemodialysis (HD) Patients
- **Study Background and Rationale:** In Europe, two calcimimetics, cinacalcet (Mimpara®) and etelcalcetide (Parsabiv®) are approved for the treatment of secondary hyperparathyroidism (SHPT) in adult patients with chronic kidney disease (CKD) receiving haemodialysis (HD) therapy. Cinacalcet was the first calcimimetic to be approved by the European Medicines Agency (EMA); marketing authorization was granted in October 2004, with posology of a starting dose of 30 mg daily, administered orally, titrating to a maximum of 180 mg daily to achieve the target intact parathyroid hormone (**PTH**) of 150-300 pg/mL, in SHPT patients. Etelcalcetide received marketing authorization from the EMA in November 2016, for intravenous (i.v.) administration of 5 mg three times weekly at the end of the HD session, adjusting dosage as necessary according to individual patient **PTH** and calcium (Ca) levels.

Data from clinical trials and real-life clinical practice have demonstrated the effectiveness of cinacalcet in reducing **PTH** levels (de Francisco et al, 2016; St Peter et al, 2009). In a controlled clinical trial comparing etelcalcetide with cinacalcet, etelcalcetide was found to be at least as effective as cinacalcet in reducing **PTH** by more than 30% after a minimum of 20 weeks' treatment, and no difference in adherence was observed (Block et al, 2017a). However, there is a lack of real-world data describing etelcalcetide medication persistence and consequently, achievement of **PTH** control. Increasingly, physicians and payers are requesting evidence of utilisation and effectiveness generated from real-world use of therapies which have received initial regulatory approval based on data obtained from strictly controlled and monitored randomised clinical trials (RCTs). To provide context, real world use of i.v. etelcalcetide as well as oral cinacalcet will be observed. This observational study will describe utilization of both calcimimetics in a contemporary population of CKD HD patients in a real-world clinical setting to provide essential data to physicians and payers.

• **Research Question and Objectives**

- How are calcimimetics used in routine practice in HD patients?

Objectives	Endpoints
Primary	

 • To describe the proportion of HD patients discontinuing calcimimetic treatment at 3-monthly intervals up to 18 months following treatment initiation 	
 • Proportion of patients discontinuing treatment at 3-monthly intervals up to 18 months following calcimimetic initiation.
Secondary	

 • To describe the characteristics of HD patients at time of calcimimetic initiation (demographics, clinical history, dialysis treatment and laboratory parameters) 	
 • Summary statistics of demographics, clinical history, dialysis treatment and laboratory parameters

 • To describe clinical management of HD patients over time (calcimimetic use, sHPT medication use, and dialysis treatment) 	
 • Summary statistics of calcimimetic use, sHPT medication use, and dialysis treatment

 • To describe levels of PTH, cCa, P and other relevant laboratory parameters in HD patients over time 	
 • Median and 25th and 75th percentile values will be described

 • To describe the proportion of HD patients achieving KDIGO (Kidney Disease Improving Global Outcomes) target for PTH over time 	
 • Proportion of HD patients achieving KDIGO target for PTH

 • To describe hypocalcemia incidence, risk factors and therapeutic responses 	
 • Hypocalcemia incidence, and summary of risk factors (ie, hazard ratios) and therapeutic responses

 • To describe the frequency of events of interest (nausea, vomiting, hospitalisations, parathyroidectomy, kidney transplant, fractures after calcimimetic initiation, and cardiovascular events) 	
 • Number of events of interest

- **Hypotheses**

Formal hypotheses will not be tested. The proportion of HD patients discontinuing calcimimetics at 3-monthly intervals up to 18 months following treatment initiation will be described.

• **Study Design/Type**

Multi-country prospective observational study

- **Study Population**

Adult patients with CKD on HD therapy initiating calcimimetic treatment (ie, calcimimetic naïve cinacalcet patients or etelcalcetide patients with or without a history of prior cinacalcet use) after site-specific etelcalcetide access (eg, known date of first drug order or date of first drug administration of etelcalcetide at study site).

- **Summary of Patient Eligibility Criteria**

Inclusion criteria

- Aged \geq 18 years and receiving HD for end-stage renal disease (ESRD) at time of calcimimetic initiation
- Patients initiating calcimimetic between date of site-specific etelcalcetide access (eg, known date of first drug order or date of first drug administration at site) to **30 November 2019** or date of site evaluation (ie, evaluation of site for study participation), **whichever occurs last**, are eligible, specifically:
 - o Calcimimetic naïve cinacalcet patients with at least one prescription for cinacalcet; or
 - o Etelcalcetide patients with or without a history of prior cinacalcet use and received at least one dose administration of etelcalcetide
- Provided informed consent or notified of participation, according to local **laws and regulations** requirements

Exclusion criteria

- No **PTH** measurement within 90 days prior to calcimimetic initiation
- Participated in a clinical trial of calcimimetic \leq 90 days of initiating calcimimetic treatment
- Previously participated in an expanded access program for etelcalcetide

- **Follow-up**

Data will be abstracted from charts. Patient chart abstraction will include 18 months of data after calcimimetic initiation and 6 months of data (eg, laboratory parameters) prior to date of calcimimetic initiation. A total of 24 months of data will be collected for each patient.

Data abstraction will be carried out either:

- part retrospective (ie data prior to patient enrolment) and part prospective (ie, data after site patient enrolment); or
- completely retrospective, specifically in countries where prospective chart abstraction is not possible (eg country-specific regulatory restrictions). Patients will be enrolled \geq 18 months after site-specific etelcalcetide access and patients may have $<$ 24 months of data abstracted.

- **Variables**

- Outcome Variables

- **Primary outcome**

- Discontinuation of calcimimetic treatment at 3-monthly intervals up to 18 months

- **Secondary outcomes**

- **Baseline**

- Demographics: age, gender, country
- Smoking history
- Clinical history: diabetes, hypertension, cardiovascular events, cardiac arrhythmia, other cardiac disease, revascularization, gastrointestinal bleed, fracture, calciphylaxis, tumoral calcinosis, cancer, parathyroidectomy, kidney transplant before calcimimetic initiation

- **Observation Period**

- Dialysis treatment: dialysis vintage, modality, access, dose, frequency, duration, dialysate calcium, ionized calcium before dialysis, net ultrafiltration, weight after dialysis, sitting heart rate before dialysis, pre-dialysis systolic and pre-dialysis diastolic blood pressure)
- Laboratory parameters: **PTH**, total serum Ca, albumin, cCa, ionized Ca, P, alanine transaminase (ALT), aspartate transaminase (AST), alkaline phosphatase, bicarbonate, bone-specific alkaline phosphatase (BAP), creatinine, C-reactive protein (CRP), ferritin, glucose, haemoglobin (Hgb), high-density lipoprotein (HDL), low-density lipoprotein (LDL), N-telopeptide (NTx), platelets, potassium, sodium, total cholesterol, total protein, white blood cell (WBC), 25OH Vitamin-D3
- Calcimimetic use: type at initiation (etelcalcetide or cinacalcet), start and end date, dose, frequency, length of prescription (for cinacalcet use only), type of prescription/administration change (dose change, drug withheld, drug discontinuation), reason for prescription change (dose titration, noncompliance, adverse event, nausea, vomiting, PTH-Low, PTH-High, PTH within target, hypocalcemia, hypercalcemia, hemodialysis discontinued, switch-to-etelcalcetide, switch-to-cinacalcet, parathyroidectomy, kidney transplant, patient refusal, safety finding, product complaint, other)
- SHPT medication use (vitamin D supplement, active vitamin D, calcium supplements, phosphate binders): medication, dose, frequency, route, date first taken and date last taken
- Achieving KDIGO target for **PTH** (ie, 2-9 times upper limit of normal (ULN) of assay)
- Incidence of hypocalcemia will be summarized in two ways: occurrence of laboratory value reporting cCa < 2.1 mmol/L; or reported adverse event due to hypocalcemia

- Number of events of interest (nausea, vomiting, hospitalisations, parathyroidectomy, kidney transplant after calcimimetic initiation, fractures, and cardiovascular events).
 - Exposure Variables
- Etelcalcetide
- Cinacalcet

- **Study Sample Size**

The analyses will be descriptive in nature. Therefore the sample size has not been assessed in terms of statistical power but rather the expected levels of precision (ie, half-width) of the 95% confidence interval (CI) for a range of rates of discontinuation following calcimimetic treatment initiation.

Based on previous studies in similar populations, the rate of cinacalcet discontinuation at 12 months is expected to be around 25% (ECHO study 24% (Urena et al, 2009 and Vervloet et al, 2010); ARO study 23.3% (de Francisco et al, 2016)). Rates of discontinuation for etelcalcetide are expected to be lower. For the purposes of estimating precision, it is assumed that rates of discontinuation will be constant throughout the study.

A sample size of 1600 is planned Data based on an interim analysis showed that the distribution of patients enrolled who were exposed to cinacalcet and etelcalcetide was observed to be 20% and 80%. The observed discontinuation rate at 12 months for cinacalcet, etelcalcetide cinacalcet-naïve and etelcalcetide switchers were 30%, 10% and 17%, respectively. A sample size of 1600 with an enrolment ratio of 1:4 cinacalcet:etelcalcetide patients would ensure that the half-width of the 95% CI for a discontinuation rate of 25-35% would result in a half-width of approximately 5% for cinacalcet. A discontinuation rate of approximately 5-20% for etelcalcetide would result in a half-width of approximately 3% (see Section 8.5).

- **Data Analysis**

There are no formal hypotheses for the study. Descriptive analyses will be performed. The proportion of patients discontinuing treatment will be described. Treatment characteristics (calcimimetic, sHPT medications and dialysis treatment) will be summarised prior to calcimimetic initiation and after hypocalcemia event. PTH, cCa, P and other relevant laboratory values over time will be summarised. The proportion of

patients achieving KDIGO target will be described. To describe time-to-event of calcimimetic discontinuation, calcimimetic interruption, hypocalcemia and calcimimetic re-initiation, Kaplan-Meier (KM) curves will be plotted and KM estimates will be calculated.

5. Amendments and Updates

Amendment or Update Number	Date	Section of Study Protocol	Amendment or Update	Reason
1	09 August 2017		See summary of changes in Appendix	
2	11 June 2019		See summary of changes in Appendix	
3	6 March 2020		See summary of changes in Appendix	

6. Rationale and Background

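### The etelcalcetide half-width of about 3% does not follow from 1,280 patients, who give 1.2–2.2%; the group size behind the figure should be stated

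*Protocol*

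**What the plan says.** The Study Sample Size paragraph in Section 4 (Abstract) sets power aside and justifies the size by the "expected levels of precision (ie, half-width) of the 95% confidence interval (CI) for a range of rates of discontinuation".

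- **Size and split:** "A sample size of 1600 is planned", and at the interim analysis "the distribution of patients enrolled who were exposed to cinacalcet and etelcalcetide was observed to be 20% and 80" percent. The precision statement then uses "A sample size of 1600 with an enrolment ratio of 1:4 cinacalcet:etelcalcetide patients".
- **Cinacalcet:** the precision is given "for a discontinuation rate of 25-35% would result in a half-width of approximately 5% for cinacalcet".
- **Etelcalcetide:** "A discontinuation rate of approximately 5-20% for etelcalcetide would result in a half-width of approximately 3" percent, with a pointer to Section 8.5.
- **Rates:** the interim 12-month discontinuation rates are 30% for cinacalcet, 10% for cinacalcet-naïve etelcalcetide patients and 17% for etelcalcetide switchers. The earlier expectation for cinacalcet, about 25%, is also a 12-month figure.
- **Time:** for the precision estimate "it is assumed that rates of discontinuation will be constant throughout the study". The primary outcome is discontinuation every 3 months up to month 18. The two rate ranges carry no time point.

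**The concern.** Expected precision is the only justification the abstract gives for 1600 patients, and it is summarised in two figures. One of them cannot be obtained from the size and split stated beside it. Someone who checks the sentence cannot tell whether 3% is an error for the whole etelcalcetide group or a correct figure for a smaller group that is not named. The distinction matters when results are read, because the precision to expect for etelcalcetide overall differs from that for naïve patients or switchers taken separately.

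A second, smaller question is whether the ranges 25–35% and 5–20%, which sit around 12-month rates, also describe the last primary time point at 18 months.

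**Working it through.** **Inputs (all from Section 4, Study Sample Size).** N = 1600; ratio 1:4, so 1600 × 0.2 = 320 on cinacalcet and 1600 × 0.8 = 1,280 on etelcalcetide; two-sided 95% interval; the rate ranges and interim rates listed above.

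**Formula.** Half-width = 1.96 × √(p(1 − p)/n).

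**Step 1: the plan's cinacalcet figure, n = 320.**

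| Rate | Half-width |
|---|---|
| 25% | 4.74% |
| 30% | 5.02% |
| 35% | 5.23% |

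The stated value of about 5% reproduces, so this formula fits the plan's own method.

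**Step 2: the etelcalcetide figure, n = 1,280.**

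| Rate | Half-width |
|---|---|
| 5% | 1.96 × √(0.05 × 0.95/1280) = 1.19% |
| 10% | 1.64% |
| 17% | 2.06% |
| 20% | 1.96 × √(0.20 × 0.80/1280) = 2.19% |
| 50% (maximum) | 2.74% |

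The stated 3% does not reproduce. Other interval methods do not close the gap: over 5–20%, Wilson gives 1.20–2.19%, and Clopper-Pearson and the continuity-corrected interval each give 1.23–2.23%. An assumed 30% loss of patients (n = 896) gives 1.43–2.62%. Conversely, a half-width of 3% at a rate of 20% needs only about 683 patients.

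**Step 3: what would give 3%.** The abstract does not state how etelcalcetide patients divide into naïve and switchers, so the splits below are assumptions.

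- Equal split, 640 each: 1.69% at 5%, 2.32% at 10%, 2.91% at 17%, 3.10% at 20%.
- 30:70, 384 naïve and 896 switchers: 3.0% for naïve patients at 10% and 2.5% for switchers at 17%. If the smaller group had a 20% rate, its half-width would be 1.96 × √(0.16/384) = 4.0%.

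So 3% is plausible as a subgroup figure, but whether it holds across 5–20% depends on a split that is not given.

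**Step 4: month 18.** Reading the constant-rate assumption as a constant hazard, the 18-month proportion is 1 − (1 − p)^1.5, where p is the 12-month proportion.

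| Group | Month 12 | Month 18 | Stated range | Half-width at month 18, complete follow-up |
|---|---|---|---|---|
| Cinacalcet | 30% | 41.4% | 25–35%: outside | 5.40% (n = 320) |
| Switchers alone | 17% | 24.4% | 5–20%: outside | 3.33% (if n = 640) |
| Naïve alone | 10% | 14.6% | 5–20%: inside | 2.74% (if n = 640) |
| Etelcalcetide pooled, equal mix | 13.5% | 19.5% | 5–20%: inside | 2.17% (n = 1,280) |

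The pooled rate reaches 20% when the switcher share w satisfies 14.6% + w × (24.4% − 14.6%) = 20%, that is w of about 0.55. Even if every etelcalcetide patient were a switcher, the pooled half-width at month 18 would be 2.35%.

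**The case against.** The strongest reply is that nothing is lost. A half-width of 1.2–2.2% is better than 3%, so the precision promised for etelcalcetide is met with room to spare. The sentence just before the precision statement reports naïve patients and switchers separately, and 640 patients per subgroup at rates of 17–20% give 2.9–3.1%, so a per-subgroup meaning is a natural guess. Section 8.5 is cited, and the contents list shows a Table 1 on precision by treatment group and discontinuation rate, which may already give the group sizes. On timing, the ranges carry no label, and if constant means the same proportion at every visit, month 18 is covered by assumption.

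Most of this stands. It limits the consequence, but it does not make the sentence right: the abstract attaches 3% to etelcalcetide without qualification and gives no other group size. The subgroup explanation is likely but unproven, and Section 8.5 and Table 1 could not be checked because the text at hand ends in Section 6.1. The same-proportion reading is hard to hold for cumulative discontinuation, although the text does not rule it out.

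Two stronger readings are tempting and should be resisted. A reader might infer that the design fails to deliver its planned precision or is too small. For the pooled group the discrepancy runs the other way. A reader might also infer that neither range covers month 18. Under a constant hazard that is true of cinacalcet and of switchers alone, but not of naïve patients, nor of pooled etelcalcetide unless switchers exceed about 55% of the group.

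**Conclusion.** The stated etelcalcetide half-width is wrong for the group it names: about 3% is stated, and 1,280 patients give 1.2–2.2% over the stated range and at most 2.7% at any rate. This rests only on the size, split and interval definition in the abstract, and on a formula that reproduces the neighbouring cinacalcet figure. The error is conservative and has no bearing on whether 1600 patients are enough. That 3% was meant for subgroups of roughly 640 is a probable explanation that the documents at hand cannot confirm.

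The month-18 point is secondary. It depends on the constant-hazard reading and, for pooled etelcalcetide, on the unknown mix. Its effect on precision is small: about 5.4% for cinacalcet with complete follow-up, against 5.0% at the interim 12-month rate. Censoring would widen this, but the text at hand gives no censoring rate.

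**What to change.** 1. Restate the etelcalcetide sentence as a pooled figure: with n = 1,280, rates of 5–20% give a half-width of about 1.2–2.2%. Alternatively, if 3% is meant for the cinacalcet-naïve and switcher subgroups, say so and give each half-width at its expected final size, which is 1,280 times the split seen at the interim analysis and not the number enrolled at that analysis.
2. Reconcile the abstract with Section 8.5 and Table 1, so that group sizes, rates and half-widths agree.
3. Label both rate ranges with the time point they describe. If they are 12-month ranges, a line for month 18 would complete the picture.

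This is a wording change with a few recalculated figures. It needs no extra patients and leaves N and the analysis as they are. If a month-18 line is added, the cinacalcet figure becomes slightly less favourable, at about 5.4% before any allowance for censoring.
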